	10.3	Informed Consent Procedure	15
	10.4	Subject Identification	16
11	TF	RIAL SPONSORSHIP AND FINANCING	16
12		RIAL INSURANCE	
13		UBLICATION POLICY	
14	RE	EFERENCES	17
5	LIS	ST OF APPENDICES	18
1	15.1	Appendix A - Zhang's curve for progression of labour included instructions	18
1	15.2	Appendix B– Questionnaire for childbirth experience, No	18
1	5.3	Appendix C – Flow chart of inclusion	
1	5.4	Appendix D – Request for participation in a research project	
1	5.5	Appendix E - Information on web-CRF_NTNU	

EXPLANATION OF TERMS

Clusters - Birth care units in Norway

Progression curve - A curve showing the expected labour progression throughout labour

Labour dystocia - A definition of when the labour progression is slower than what is expected to be normal

Labour stages:

Latent first stage – painful contractions and some cervical change including cervical effacement and dilatation up to 4 cm

Established first stage – regular painful contractions and progressive cervical dilatation ≥ 4 cm

Passive second stage - full dilatation of the cervix prior to or in the absence of involuntary compulsive contractions.

Active second stage - Time from start of active pushing to delivery (1)

Local coordinator - Midwife responsible for the trial at each birth care unit

[figure not shown]
Robson group I – Nulliparous women with a singleton vertex fetus and spontaneous onset of labour, gestational age ≥37 weeks

1 INTRODUCTION

1.1 Background

There is no worldwide consensus on duration of labour after spontaneous onset of labour, and therefore, there is no consensus on the definition of prolonged labour (labour dystocia). The progression of labour is traditionally measured by the dilatation of the cervix over time, but the expected progression per time unit varies between and within countries. The duration of labour and labour curve patterns are still subjects to discussion (2).

In 1954, Emanuel Friedman presented the first progression curve based on labour course data on 100 nulliparous women (Figure I) (3). Friedman's curve has been widely adopted and applied in clinical practice internationally for almost 60 years. In 2002, [name] presented an alternative labour curve based on 1329 low-risk women with spontaneous onset of labour (Figure II) (4). Zhang's replicated these findings in a large cohort of 26,838 women in 2010 (5).

[figure not shown]

Figure I. Emanuel Friedman's curve of cervical dilatation in nulliparous women (1954)

Figure II. [name]'s curve of cervical dilatation (2010)

Zhang's curve differs distinctly from the Friedman's curve in that the cervix dilate substantially slower, especially before reaching six centimetres of dilatation, nor is the deceleration phase in Friedman's curve found in Zhang's curve. These findings may suggest that the diagnostic criteria for labour dystocia following Friedman's curve are too stringent in contemporary birth care.

Labour dystocia is characterised by abnormally slow progression of the labour process and is among the most common challenges of birth care especially in nulliparous women (6,7), as labour dystocia is the most common reason for emergency caesarean sections (8).

Labour dystocia is most often initially treated with amniotomy, followed by oxytocin infusion to augment the contractions of the uterus. Oxytocin is a potent drug and is classified by the Institute for Safe Medication Practices, US, as one out of 12 medications, which is "bearing heightened risk of harm" (9). Even when used correctly, oxytocin is found associated with increased risk of instrumental vaginal delivery, episiotomy (10), emergency caesarean section, sphincter ruptures, low Apgar score, low pH in neonates, and transfer of the new-born to a neonatal intensive care unit (11). If augmentation with oxytocin does not lead to an adequate effect on labour progression, a caesarean section is performed. An uncomplicated vaginal birth in nulliparous women strongly predicts uncomplicated labour and delivery in subsequent pregnancies (12), while emergency caesarean sections are associated with lower rates of breastfeeding, and increased risk of post partum depression (13), anaemia, hysterectomy (14), stillbirth and uterine rupture in subsequent pregnancies and deliveries (15). Neonates delivered by caesarean section have an increased risk of respiratory distress post partum (16) and infant asthma and allergies (17).

1.2 Rationale for the trial

Nulliparous women with a singleton vertex infant and spontaneous onset of labour at term are usually considered at low-risk of adverse birth related outcomes, and, thus, they have a considerable potential of spontaneous course of labour without interventions. Even so, the rate of augmentation with oxytocin in low-risk nulliparous women is high in Scandinavia. Over the last decade the rate in Norway has been reported in research articles to be from 44 to 62 % (10,18,19). High rates of oxytocin augmentation have not been found to reduce caesarean section rates or to improve birth related outcomes for mother or baby. (6) The rates of emergency caesarean sections in low-risk nulliparous women with spontaneous onset of labour were about 9 % in Norway (20) in 2012.

A graphic record of labour progression, often called a partogram, is widely used. A partogram enables midwives and doctors to monitor labour progression during the course of labour, and, according to a certain set of criteria for labour dystocia, to carry out necessary interventions. In Norway the expected progression of labour is close to linear and based on interpretations of Friedman's curve (Figure I) (3). The definition of labour dystocia varies from institution to institution; although a definition in accordance with WHO recommendations is widely used and recommended by the Norwegian Society in Obstetrics and Gynecology (when cervical dilatation crosses the 'action line' 4 hours from the 'alert line'). The evidence of the definition is vague, and contemporary research has shown that normal labour can last substantially longer, especially at an early stage of labour without jeopardising outcomes for the mother or neonate (8,21). A new dynamic guideline for labour progression is developed according to contemporary research findings by Zhang et al. (21). This guideline differs from guidelines based on an interpretation of Friedman's research by not expecting a linear progression and by defining the progression to be normal if the rate of cervical dilatation is within the 95 percentile of the duration in Zhang's material of spontaneous labours (Appendix A).

2 STUDY OBJECTIVES AND RELATED ENDPOINTS

The main aim of this trial is to evaluate in what way two different guidelines for diagnosing labour dystocia, one based on and interpretation of Friedman's research, and one based on Zhang's research of labour progression, affect maternal and neonatal outcomes related to delivery among nulliparous women with a singleton vertex infant and spontaneous onset of labour, gestational age ≥37weeks. Overall we wish to monitor and document procedures and outcomes in relation to the labour process.

2.1 Primary Endpoint

The rate of emergency caesarean sections

2.2 Secondary Endpoints

- The rate of oxytocin augmentation during labour
- The rate of instrumental vaginal deliveries
- The rate of artificial rupture of membranes (amniotomy)
- The rate of electronic fetal monitoring (CTG or CTG+STAN)
- The rate of epidural analgesia
- The rate of episiotomies
- The rate of perineal tears grade 3 and 4
- The rate of dystocia
- Postpartum haemorrhage
- Blood transfusion
- Apgar scores
- Ph in the umbilical artery
- The rate of transfers of neonates to the Neonatal Intensive Care Unit (NICU)
- Mean score of women's experience with child birth (measured by :"The Childbirth Experience Questionnaire, CEQ" (22), (Appendix B)
- Mean duration of labour (active phase of first stage, latent phase of second stage, expulsion phase and second stage in total)
- Detailed measures of oxytocin augmentation (mean length of augmentation, dosage, and administration throughout labour)

We will also register the following variables:

Indications for interventions, cervical dilatation at onset of oxytocin augmentation and amniotomy, reason for admittance and length of stay in NICU and compliance with the protocol.

3.2 Number of Participants

We expect to collect data on 6582 deliveries from the cluster birth care units for analysis on an individual level. This corresponds to approximately 470 per cluster. The design allows for flexibility, so that larger birth care units may contribute with more study subjects than smaller units.

3.3 Inclusion Criteria

Norwegian birth care units (>500 deliveries per year) that are willing to adhere to the allocated guideline for all Robson group I women during the study period, and who consider that they have the capacity to participate both logistically and in practice.

4 OVERALL STUDY DESIGN

4.1 Hypothesis

We hypothesise that adhering to the guideline for labour progression presented by [name] (21) (figure II) will decrease the rate of emergency caesarean sections and augmentation with oxytocin among low-risk nulliparous compared to adhering to guidelines for labour progression based on a modified Friedman's curve (3) (figure I), without jeopardising the outcome for mother or neonate.

In this multicenter trial we include 14 birth care units Norway. Each cluster will be randomly allocated to either intervention or control arm.

Intervention - Labour progression guideline in the intervention clusters (Zhang's guideline, Z):

During established first stage of labour, i.e. regular painful contractions and cervical dilatation ≥ 4 cm (1), dystocia is diagnosed if the cervix dilatation rate does not meet the expected progression according to Zhang's findings (Appendix A). During second stage of labour, dystocia is diagnosed, if the time from full dilatation to active expulsion phase (passive second stage) exceeds 1 hour and 45 minutes (2 hours and 30 minutes for women with epidurals), or if the expulsion phase (active second stage) exceeds 60 minutes. This progression curve is based on contemporary research on labour progression by [name] (Appendix A).

Control - Labour progression guideline in the control clusters (based on Friedman's guideline, F): During established first stage of labour, i.e. regular painful contractions and cervical dilatation from 4 cm (1), dystocia is diagnosed if cervix dilatation rate is less than 1 centimetre per hour assessed after 4 hours (crossing the 4-hours action line). During second stage of labour, dystocia is diagnosed if the time from full dilatation to active expulsion phase (passive second stage) exceeds exceeds 1 hour (2 hours for women with epidurals), or if the expulsion phase (active second stage) exceeds 60 minutes.

The randomisation process will be performed through a central computer assisted programme which stratifies by number of deliveries and the rate of caesarean sections for Robson group I at each unit per year. The trial will be conducted according to the CONSORT statement for planning and implementation of cluster randomised trials (23).

We believe that cluster randomisation, i.e. randomisation at hospital level, is superior to individual randomisation as choosing individual randomisation for this specific study would imply substantial risk of contamination.

Estimated activities in the trial period:

		2014/2015				2015/2016				2016/2017			
Activity	Q3	Q4	Q1	Q2	Q3	Q4	Q1	Q2	Q3	Q4	Q1	Q2	
Inclusion and randomisation of clusters													
Guideline instructions at clusters													
Enrolment of participants				E to			1						
Patient satisfaction questionaire				7	VIS.	 							
Control of data							W						
Data analyses								Ext	4.5				
Production and publication of articles								1/18					
Final report to policy makers										1 7			

4.2 Test of the applicability of Zhang's guideline

We will test the applicability of Zhang's guideline for labour progression with respect to the understanding and the use of the guideline during labour. A small number of midwives will be asked to participate in testing the guideline. They will receive Zhang's guideline for labour progression along with written instructions about how to use the guideline, and a number of constructed labour cases on which they can test the applicability of the guideline. Afterwards the midwives are invited to participate in a workshop with the PI. In the workshop the midwives will be encouraged to share experiences from their work with the guideline and go through each case example and the guideline together with the PI. Experiences and comments from the midwives will then be used to adjust guideline, written instructions, and the protocol, if needed.

5 STUDY PROCEDURES

5.1 Flow Chart

See appendix C for flow chart of cluster inclusion and expected number of individuals for analysis.

5.2 Invitation to Clusters

All eligible clusters in Norway will receive a concise edition of the protocol and a written invitation to participate in the trial.

5.2.1 Cooperation agreement

A cooperation agreement must be signed by each cluster at inclusion. Each cluster must provide one local coordinator, who will be responsible for the trial during the study period (see point 5.4).

5.2.2 Baseline data

The following baseline data will be collected for each cluster:

- Number of Robson Group 1-deliveries in 2012
- The rate of emergency caesarean sections in Robson Group 1 in 2012

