8.2 Randomisation

8.2.1 Allocation-sequence generation

Key elements to specify regarding allocation of treatment are:

- The method of generating the allocation sequence is computer-generated
- The allocation ratio is equal to one
- The type of randomisation is restricted
- The factor; size of birth care unit and rate of emergency caesarean sections will be used for stratification

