13 PUBLICATION POLICY

All colleagues, who have contributed significantly with the planning and/or performance of the study (Vancouver convention 1988), may be included in the list of authors.

Preliminary planned publications:

- Paper 1: The Labour Progression study, evaluating the use of a new partogram in labour care for low-risk nulliparous women. A protocol of a cluster randomised trial in Norway
- Paper 2: Is it possible to reduce the rate of emergency cesarean section in low-risk nulliparous without compromising maternal and fetal health? A cluster randomised trial
- Paper 3: Is it possible to reduce the rate of augmentation in low-risk nulliparous without compromising maternal and fetal health? - A cluster randomised trial
- Paper 4: How does the amount of oxytocin during labour affect the outcome in neonates? A cohort of low-risk nulliparous women
- Paper 5: The use of oxytocin and labour progression in obese women.— A cohort of low-risk nulliparous women
- Paper 6: Does the expected labour progression according to contemporary research, correlate with labour progression in low-risk nulliparous women? A cohort of low-risk nulliparous women
- Paper 7: Low-risk nulliparous women's childbirth experience labour according to two guidelines for expected progression of labour A cluster randomised trial

Ownership and use of data:

The ownership of the data generated at each unit belongs to each of the included hospitals. The project group has managerial prerogative over the data entered into the web based case report form, designed for this study. The managerial prerogative is not in hindrance with each hospital's right to publish their own data after

publication of planned articles, provided that it is not in conflict with planned publications. Provided that the criteria for authorship is fulfilled, according to the International Committee of Medical Journal Editors (ICMJE), one author from each hospital is invited to participate as co author of one of the planned publications.

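### The unit-level baseline omits the oxytocin augmentation rate, although less augmentation is part of the hypothesis; the cost is precision and interpretability of that comparison, not its validity

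*Protocol*

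**What the plan says.** Section 5.2.2 lists two baseline items per unit, "Number of Robson Group 1-deliveries in 2012" and "The rate of emergency caesarean sections in Robson Group 1 in 2012", and nothing else. They correspond to the two stratification factors in section 8.2.1, unit size and emergency caesarean rate. The individual baseline list in section 5.3.2 (age, height, weight, civil status, education, smoking, gestational age) says nothing about a unit's augmentation practice.

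Augmentation nevertheless has a prominent place. Section 4.1 hypothesises that the new guideline "will decrease the rate of emergency caesarean sections and augmentation with oxytocin among low-risk nulliparous". Section 2.2 opens its list of secondary endpoints with "The rate of oxytocin augmentation during labour". In section 13, Paper 3 is a cluster-randomised report asking "Is it possible to reduce the rate of augmentation in low-risk nulliparous without compromising maternal and fetal health".

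On pre-trial practice, section 1.2 states: "Over the last decade the rate in Norway has been reported in research articles to be from 44 to 62" per cent. It adds that institutions define labour dystocia differently.

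**The concern.** Units probably enter the trial with different augmentation habits, and only 14 of them are randomised. Stratifying on size and caesarean rate balances augmentation only so far as it is related to those two factors. Without a unit baseline, the report cannot show whether the arms started level on one of the two outcomes in the hypothesis. It also cannot use a covariate likely to predict that outcome well. Section 5.4 has the allocated guideline introduced at every unit, control units included, so practice may shift in both arms. A reader of Paper 3 would want to know how far an observed difference comes from a fall in one arm, a shift in the other, or a difference already present.

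The choice of covariates can be left to an analysis plan, but the list of data to be collected is a protocol matter. An analysis plan cannot adjust for something nobody gathered.

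A smaller point is the age of the baseline. The timetable under section 4.1 begins in 2014/2015, so the 2012 figures will be roughly two years old or more. The bars of the chart are not legible in the text at hand, so the quarter of randomisation cannot be read.

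**Working it through.** The protocol gives no precision or power figure for augmentation, so there is none to reproduce. The sample size in section 8.1 concerns emergency caesarean section, and this point does not depend on it.

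**Inputs from the protocol**
- Units: "In this multicenter trial we include 14 birth care units Norway" (section 4.1).
- Allocation: "The allocation ratio is equal to one" (section 8.2.1). Hence 14 / 2 = 7 units per arm; this is derived, not stated.
- Reported augmentation rates: 44 to 62% (section 1.2), a range of 18 points.

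**Assumed inputs**
- Between-unit SD of the augmentation rate. Reading the range as plus or minus 2 SD gives 18 / 4 = 4.5 points; 3 to 6 is tried around it. Reading it as plus or minus 1 SD gives 18 / 2 = 9 points.
- Correlation r between a unit's baseline and trial-period rates: 0.7, with 0.5 to 0.8 tried.

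**Step 1. Chance difference between arms.** SE = SD × sqrt(1/7 + 1/7) = SD × 0.5345. The 95% range is 1.96 × SE. The last column uses the normal distribution.

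| SD (points) | SE | 95% range | Chance of a difference beyond 5 points |
|---|---|---|---|
| 3 | 1.60 | ±3.1 | 0.2% |
| 4.5 | 2.41 | ±4.7 | 4% |
| 6 | 3.21 | ±6.3 | 12% |
| 9 | 4.81 | ±9.4 | 30% |

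**Step 2. Adjustment for the unit baseline.** Adjusted SE = SE × sqrt(1 − r²). For SD 4.5:
- r = 0.5: 2.41 × 0.866 = 2.08
- r = 0.7: 2.41 × 0.714 = 1.72
- r = 0.8: 2.41 × 0.600 = 1.44

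At r = 0.7 the variance falls by r² = 49%; at r = 0.5 it falls by 25%. For SD 9 and r = 0.7, the SE goes from 4.81 to 3.44.

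**Step 3. Price of the covariate.** With 14 units an unadjusted comparison of unit rates has 14 − 2 = 12 degrees of freedom, and one covariate leaves 11. The net gain is therefore slightly smaller than step 2 shows.

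The formulas ignore the stratification, which would reduce the chance difference if augmentation is related to size or caesarean rate.

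**The case against.** The strongest reply is that nothing is broken. Units are randomised, and section 8.4 plans a significance test for dichotomous variables that allows for clustering. The between-unit variation behind step 1 is what such a test carries. A reader might infer that a pre-trial difference would simply be mistaken for a guideline effect, or that the comparison is biased. The documents do not support that: a valid cluster analysis already allows for chance imbalance. This part of the reply stands in full.

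A reader might also infer that imbalance could never be detected or corrected. That goes too far as well. Section 7.1 has labour care recorded as usual in the electronic medical record, and section 8.3 permits changes to the plan until database lock, so unit rates might be retrieved later. What remains is that the period and definition would then be chosen after allocation is known; fixing them beforehand avoids that. For emergency caesarean section the inference fails outright, since its unit baseline is collected and stratified on.

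The size is also open to challenge. The 44 to 62% comes from separate research articles over a decade, not from these 14 units. Because each arm follows one common guideline (sections 4.1 and 5.3), pre-trial rates may predict trial-period rates less well than r = 0.7 assumes. Both criticisms stand, which is why the figures are an illustration with a range.

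Finally, augmentation is a secondary endpoint, and the two baseline items match the stratification factors, so the section is internally consistent. That is true, and it limits the weight of the point. It does not explain why an outcome named in the hypothesis has no unit baseline when one is cheap to obtain.

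**Conclusion.** The point holds as a missed gain in precision and interpretability for one key secondary outcome. It is not a source of bias, and the primary endpoint is unaffected.

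On the assumed SD of 4.5 points, chance alone gives a between-arm difference with a standard error of about 2.4 points, and a baseline correlated 0.7 would bring this to about 1.7, before the small loss from one degree of freedom. At r = 0.5 the gain is modest (2.1). On the wider SD of 9 points, both the chance difference and the absolute gain double. The SD and the correlation are assumptions that the documents can neither confirm nor exclude. What the documents do establish is that no unit augmentation rate is planned. No consequence of the 2012 date has been quantified; it is a reason to refresh the figures while the extract is being made, and no more.

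**What to change.** Extend section 5.2.2 so that each unit supplies, for the latest complete 12 months before randomisation, its Robson group I oxytocin augmentation rate and emergency caesarean rate, by one common definition and from existing records. Report both by arm. Pre-specify, in the protocol or the analysis plan, the unit's baseline augmentation rate as a covariate in the augmentation comparison.

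The cost is 14 aggregate extracts, some coordinator time, and one degree of freedom out of 12. Historical recording of augmentation may be less uniform than in the web-CRF; that would weaken the correlation and reduce the gain.

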8 STATISTICAL METHODS AND DATA ANALYSIS

8.1 Determination of Sample Size

The determination of the sample size (number of clusters and individuals for analysis) is based on a power calculation with the least occurring primary outcome; emergency caesarean section, which is 9.2 % in the study population (p1). Further, we expect that the emergency caesarean section rate will be 6.9 % (p2) when using the new guideline for labour progression.

Formula (4) on page 320 in the article by Hayes et al. (24) is used to calculate the needed number of clusters and participants. According to this formula, with a chosen significance level of 0.05, a power of 80 % and p1=9.2 % and p2=6.9 %, we will have to include at least 14 clusters using the allocated guideline in 6582 Robson group I women.

All statistical analysis will be conducted in STATA, SPSS or similar statistical software.

In the 14 clusters there will be approximately 8000 women fulfilling the inclusion criteria per year (2012). With an expected inclusion of 90 % and a dropout of 10%, the required numbers of women should be included within 10-12 months.

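### The only baseline caesarean rate collected per unit is the single year 2012; pooling three recent years and adjusting for the pooled rate would be a cheap gain in precision, though the present plan is not an error

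*Protocol*

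**What the plan says.** Section 5.2.2 lists two unit-level baseline items, both for one calendar year: "Number of Robson Group 1-deliveries in 2012" and "The rate of emergency caesarean sections in Robson Group 1 in 2012". No other unit-level caesarean rate is collected before the trial.

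Section 8.2.1 gives the stratification factors: "size of birth care unit and rate of emergency caesarean sections will be used for stratification". Section 4.1 says that the randomisation programme "stratifies by number of deliveries and the rate of caesarean sections for Robson group I at each unit per year". Neither names the year. That the 2012 figure is meant is the natural reading, because it is the only one collected, but it remains an inference.

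Section 8.1 supplies the rest: about 8000 eligible women a year in the 14 units (2012), caesarean rates of 9.2 % and 6.9 %, significance level 0.05, power 80 %, and 6582 women. Section 3.2 gives about 470 women per unit. Section 8.4 promises a test that allows for clustering and does not say whether a unit-level baseline covariate enters it.

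**The concern.** The stratifier is the baseline value of the primary endpoint, and only 14 units are randomised. Baseline information on the units is therefore one of the few tools for making the arms comparable and for removing between-unit variation from the treatment comparison. A rate from one year carries the binomial error of that year. If that error is large relative to the true differences between units, the strata partly sort units by chance, and a covariate built from the same rate explains little. The activity table opens in Q3 of 2014/2015, so the end of 2012 lies at least about 1.5 years before randomisation and its midpoint about two. At stake is some balance and a few points of power. The validity of the comparison is not in question.

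**Working it through.** **Precision of the 2012 rate.** 8000 / 14 = 571 women per unit-year; 571 × 0.092 = 52.6 events. Standard error = √(0.092 × 0.908 / 571) = 1.21 points, a 95 % half-width of 2.4 points, against a target effect of 9.2 − 6.9 = 2.3 points. Three pooled years give 1.21 / √3 = 0.70 points.

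**The k implied by the sample size.** The protocol states no k or intracluster correlation, so its figure can be solved for k but not confirmed. The standard cluster formula, taken here to be the one cited (two-sided test assumed), is

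c = 1 + (1.96 + 0.84)² × [p1(1−p1)/n + p2(1−p2)/n + k²(p1² + p2²)] / (p1 − p2)².

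With c = 7 per arm and n = 6582/14 = 470, this gives k = 0.083; without the leading 1 it gives k = 0.109.

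**Share of signal in the observed unit rate.** For y years, reliability = k² / [k² + 0.908 / (571 × y × 0.092)].

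| k | one year | three years | noise, one year |
|---|---|---|---|
| 0.083 | 0.28 | 0.54 | 72 % |
| 0.109 | 0.41 | 0.67 | 59 % |
| 0.131 | 0.50 | 0.75 | 50 % |
| 0.20 | 0.70 | 0.87 | 30 % |

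The break-even is k = √[0.908 / (571 × 0.092)] = 0.131 at average size. It is about 0.18 for a unit with 300 eligible women and 0.10 for one with 1000.

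**Power with the rate as a unit-level covariate.** On the scale of the sample size formula, the variance of the arm difference is

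V = [(0.0835 + 0.0642)/470 + (1 − reliability) × k² × (0.092² + 0.069²)] / 7,

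tested with noncentral t on 11 df (12 df and reliability 0 without a covariate). At k = 0.083 the standard error is 0.736 points with one year and 0.713 with three, so the noncentrality is 0.023/0.00736 = 3.12 and 0.023/0.00713 = 3.23.

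| k | no covariate | one year | three years |
|---|---|---|---|
| 0.083 | 79.2 % | 81.1 % | 83.5 % |
| 0.109 | 73.0 % | 78.3 % | 82.5 % |

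Three years against one gain 2.4 and 4.2 points; three years against no covariate gain 4.3 and 9.5.

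**Power with stratification only.** Simulation with 14 equal units, two rate strata and an unadjusted cluster-level t-test gave 79.2 % with one year against 79.5 % with three (k = 0.083), and 73.1 % against 73.9 % (k = 0.109). The standard deviation of the arm imbalance in true unit rates at k = 0.083 was 0.41 points unstratified, 0.37 with one year and 0.34 with three. At k = 0.131 it was 0.64, 0.53 and 0.48.

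**Drift.** Let the correlation of a unit's true rates fall geometrically with the gap in years, with adjacent-year correlation r, and let 2015 stand for the trial period (both assumptions). The share of trial-period variation that 2012 alone explains is r⁶ × reliability. For the 2011–2013 mean it is [(r⁴ + r³ + r²)/3]² / [(3 + 4r + 2r²)/9 + (1/reliability − 1)/3], with the one-year reliability inserted; for 2012–2014 the bracketed numerator is r³ + r² + r.

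| k = 0.083 | 2012 | 2011–2013 | 2012–2014 |
|---|---|---|---|
| r = 1.0 | 0.28 | 0.54 | 0.54 |
| r = 0.9 | 0.15 | 0.31 | 0.38 |
| r = 0.8 | 0.08 | 0.16 | 0.25 |

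Inserting the r = 0.8 row for reliability in V gives power of 79.2, 80.0 and 80.8 %. Drift shrinks the gain and does not reverse it in this range.

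**The case against.** The strongest reply is that nothing here is misstated. Stratifying on a noisy rate is valid, and in the simulation it still balanced the arms better than no stratification. The ethics reference is numbered 2013/1862, so 2012 was plausibly the latest complete year when the protocol was prepared. All of that stands, and it makes this a suggestion for improvement.

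A second reply is that the gain depends on an analysis the protocol does not describe. This also stands: the documented use of the rate is stratification, where the power gain is under one point at the implied k. A normal approximation to a similar simulation gave up to about 3 points at larger k. Whether a covariate is used may properly be settled in the statistical analysis plan, which is not at hand, so its absence from section 8.4 is no fault.

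A third reply is that three complete years before a 2014 randomisation are 2011–2013, centred on the same point as 2012. That is true, so the pooled rate need not be fresher. The benefit then comes from three times the events, and the drift check shows that it survives.

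A reader might also infer that the 2012 rate is mostly noise as a matter of fact. The protocol does not support this: k is not given, and the statement fails above about 0.13. Nor should the larger gain calculated at k = 0.20, from 72 to 81 % power, be used as the headline. It belongs to a setting in which the one-year rate is already 70 % signal.

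**Conclusion.** The point holds as a cheap improvement of minor weight. One year of data gives each unit's rate a standard error of 1.2 points. If the between-unit variation is what the sample size implies (k about 0.083 to 0.11), 59 to 72 % of the observed spread between units is chance. Three pooled years, used both for stratification and as a unit-level covariate, add about 2 to 4 points of power over a one-year covariate and about 4 to 10 over no covariate. For stratification alone the benefit is slightly better balance and less than one point of power.

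These figures assume equal unit sizes, stable unit rates, a two-sided 5 % test, a k solved from the sample size, and that the 2012 rate is indeed the stratifier. Drift in unit rates reduces the gain. The result does not show that the planned randomisation is flawed.

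**What to change.** In section 5.2.2, replace the two 2012 items with the number of Robson group I deliveries and the number of emergency caesareans in each of the last three complete calendar years before randomisation. In section 8.2.1, name the pooled rate over those years as the stratification value, and let section 4.1 refer to the same value. In section 8.4 or the statistical analysis plan, adjust the primary analysis for the pooled rate as a unit-level covariate; most of the gain depends on this step.

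The cost is a request to each unit for two further years of the same figures, and one of 12 degrees of freedom for the covariate (already counted in the power figures above). The protocol does not say whether those years are available for every unit, so this should be checked first. Where a unit can supply only two years, pooling two still raises reliability, from 0.28 to 0.44 at k = 0.083.
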